## **Site Operations Manual (SOM)**

A Site Operations Manual (SOM) accompanies this protocol, providing the operational details for study conduct.

### **Notification of serious adverse events**

Refer to [Section 9.2](#) of the protocol for definitions and reporting requirements for Serious Adverse Events (within 24 hours after awareness of the SAE to the local Novartis Drug Safety and Epidemiology Department and notify the Clinical Trial Leader.).

Contact information is listed in the SOM.

## List of abbreviations

AChR	Acetylcholine Receptors
ADA	Anti-drug antibodies
ADCC	Antibody dependent cell mediated cytotoxicity
AE	adverse event
ALT	alanine aminotransferase
ALP	alkaline phosphatase
aPTT	activated partial thromboplastin time
AST	aspartate aminotransferase
BMI	Body Mass Index
BUN	blood urea nitrogen
CD-ROM	compact disc – read only memory
CDC	Complement dependent cytotoxicity
CFR	Code of Federal Regulation
CI	cholinesterase inhibitor
CI	confidence interval
CK	creatinine kinase
CRF	Case Report/Record Form (paper or electronic)
CRP	C-Reactive Protein
CTL	Clinical trial leader
CO 2	carbon dioxide
CRO	Contract Research Organization
CSR	Clinical Study Report
CV	coefficient of variation
EC	Ethics committee
ECG	Electrocardiogram
EDC	Electronic Data Capture
ELISA	Enzyme-linked immunosorbent assay
DLTs	dose limiting toxicities
FAS	full analysis set
FDA	Food and Drug Administration

GCP	Good Clinical Practice
GLP	Good Laboratory Practice
$\gamma$ -GT	Gamma-glutamyl transferase
h	hour
HIV	human immunodeficiency virus
IA	Interim Analysis
ICH	International Conference on Harmonization of Technical Requirements for Registration of Pharmaceuticals for Human Use
IEC	Independent Ethics Committee
IgG	Immunoglobulin G
IgM	Immunoglobulin M
IN	Investigator Notification
i.v. or IV	Intravenous
IRB	Institutional Review Board
IRT	Interactive Response Technology
IUD	intrauterine device
IUS	intrauterine system
KLH	keyhole limpet hemocyanin
LFT	Liver function test
LDH	lactate dehydrogenase
LLOQ	lower limit of quantification
MedDRA	Medical dictionary for regulatory activities
mg	milligram(s)
MG	Myasthenia gravis
MG-ADL	Myasthenia Gravis Activities of Daily Living Scale
MGC	Myasthenia Gravis Composite
MG QOL-15	Myasthenia Gravis Quality of Life
ml	milliliter
MM	minimal manifestation
MMF	Mycophenolate mofetil
MPA	Mycophenolic acid
MuSK	Muscle Specific Kinase

nAChR	nicotinic acetylcholine receptor
NHP	non-human primate
NOAEL	No observed adverse effect level
PA	posteroanterior
PBMC	peripheral blood mononuclear cell
PD	pharmacodynamic(s)
PoC	Proof of Concept
PK	pharmacokinetic(s)
PT	prothrombin time
PTT	partial thromboplastin time
QMG	Quantitative Myasthenia Gravis
RA	Rheumatoid Arthritis
RBC	red blood cell(s)
REB	Research Ethics Board
SAE	serious adverse event
s.c. or SC	subcutaneous
SGOT	serum glutamic oxaloacetic transaminase
SGPT	serum glutamic pyruvic transaminase
SD	standard deviation
solCD40	soluble CD40
SOM	site operations manual
SUSAR	Suspected Unexpected Serious Adverse Reactions
TBL	total bilirubin
TE	thromboembolic events
TEG	thromboelastography
totCD40	total CD40 (free CD40 and bound CD40)
TTx	tetanus toxoid
ULN	upper limit of normal
ULOQ	upper limit of quantification
WBC	white blood cell(s)
wk	week
WHO	World Health Organization

### Pharmacokinetic definitions and symbols

AUC tau	The area under the plasma concentration-time curve from time zero to the end of the dosing interval tau [ $\mu\text{g} \times \text{day} / \text{mL}$ ]
AUC tau,ss	The area under the plasma concentration-time curve from time zero to the end of the dosing interval tau, at steady state [ $\mu\text{g} \times \text{day} / \text{mL}$ ]
C av,ss	The average steady state plasma concentration during multiple dosing [ $\mu\text{g} / \text{mL}$ ]
C max	The observed maximum plasma concentration following drug administration [ $\mu\text{g} / \text{mL}$ ]
C max,ss	The observed maximum plasma concentration following drug administration at steady state [ $\mu\text{g} / \text{mL}$ ]
C min,ss	The lowest plasma concentration observed during a dosing interval at steady state [ $\mu\text{g} / \text{mL}$ ]
T max	The time to reach the maximum concentration after drug administration [day]

Corporate Confidential Information

Corporate Confidential Information

Corporate Confidential Information

## Protocol synopsis

Protocol number	CCFZ533X2204
Title	A multi-center, randomized, double-blind, placebo-controlled, parallel group study to preliminarily evaluate the safety, tolerability, pharmacokinetics and efficacy of CFZ533 in patients with moderate to severe myasthenia gravis
Brief title	Safety, tolerability, pharmacokinetics and efficacy of CFZ533 in moderate to severe myasthenia gravis patients.
Sponsor and Clinical Phase	Novartis Phase IIa
Intervention type	Drug
Study type	Interventional
Purpose and rationale	This study is designed to preliminarily evaluate safety, tolerability, pharmacokinetics/pharmacodynamics and efficacy of CFZ533 as an add-on therapy to standard of care in patients with moderate to severe myasthenia gravis (MG).  The results of this study will provide preliminary data to evaluate a further development of CFZ533 in the treatment of myasthenia gravis.
Primary Objective(s)	To evaluate the safety and tolerability of CFZ533 as an add-on therapy to standard of care in moderate to severe MG patients.  To evaluate the efficacy of IV CFZ533 as an add-on therapy to standard of care in patients with moderate to severe MG after 24 weeks of treatment.
Secondary Objectives	To evaluate the efficacy of CFZ533 throughout the 24 weeks treatment period and the decay in efficacy throughout the 24 weeks follow-up period. To evaluate changes in patient's quality of life (QOL) throughout 24 weeks the treatment period. To evaluate the pharmacokinetics of CFZ533 To evaluate the pharmacodynamics of CFZ533 To assess immunogenicity of CFZ533
Study design	This is a randomized, double-blind, placebo controlled, non-confirmatory study in MG patients administered IV CFZ533 over a 24 weeks treatment period followed by other 24 weeks safety follow-up period.
Population	A total of approximately 44 male and female patients aged 18-85 (inclusive) years will be randomized in this study.
Inclusion criteria	Key inclusion criteria are listed:  Diagnosis of MG class IIa to IVa inclusive (Myasthenia Gravis Foundation of America Clinical Classification).  Quantitative Myasthenia Gravis (QMG) score of 10 or greater. If the QMG score is < 15 no more than 4 points may be derived from items 1 or 2 (ocular motility disturbance and ptosis).  Presence of acetylcholine receptor (AChR) or Muscle Specific Kinase (MuSK) autoantibodies based on medical history and confirmed by autoantibodies diagnostic test performed at screening.


Inclusion criteria (cont'd)
	
Only one immunosuppressant or immunomodulatory drug at a stable dose is allowed during the study (i) azathioprine and mycophenolate mofetil must be stable for at least 4 months prior to randomization (ii) cyclosporine must be stable for at least 3 months prior to randomization.
 
If the patient is on oral corticosteroids, methotrexate or tacrolimus at screening, the dose must be stable for at least 1 month prior to randomization.
 
If the patient is on cholinesterase inhibitors at screening, the dose must be stable for at least 2 weeks prior to randomization.
 
Women of child-bearing potential, defined as all women physiologically capable of becoming pregnant, may be included in the study if they are using highly effective methods of contraception during the study and for 12 weeks after study treatment.

Exclusion criteria
	
Key exclusion criteria are listed:
 
MGFA grade I, IVb, or V disease.
 
Documented presence of unresected thymoma.
 
Patients having undergone thymectomy or thymo thymectomy (resection of thymoma) within 6 months of screening.
 
Patients having received any of the following treatments prior to randomization:
 
IVIg or plasma exchange within 8 weeks;
 
oral or IV cyclophosphamide treatment within 3 months;
 
IV corticosteroid bolus (dose higher than 1 mg/kg) within 3 months;
 
belimumab within 6 months. For patients who received belimumab earlier, B cell count should be within normal range;
 
rituximab within 12 months. For patients who received rituximab earlier, B cell count should be within normal range;
 
any other biologic or an investigational drug within 1 month or five times the half-life, whichever is longer.
 
Live vaccines within 4 weeks of study drug infusion.
 
Patients who are at significant risk for TE as judged by the investigator or have any one of the following:
 
History of either thrombosis or 3 or more spontaneous abortions with or without the presence of anti-cardiolipin autoantibodies;
 
Presence of prolonged partial thromboplastin time (PTT).

Investigational and reference therapy
	
CFZ533 10 mg/kg IV infusion CFZ533 matching placebo IV infusion

Efficacy/PD assessments	Efficacy assessments: Quantitative Myasthenia Gravis (QMG) Score Myasthenia Gravis Composite (MGC) Score Quality of life questionnaires: MG-ADL and MG QOL-15 Pharmacodynamics assessments: Corporate Confidential Information
Safety assessments	Physical examination AEs Vital signs ECGs Hematology, blood chemistry, urinalysis Corporate Confidential Information
Data analysis	Analysis methods  The primary efficacy variable is the change from baseline in QMG score after 24 weeks of treatment (at week 25 visit). The changes from baseline in QMG scores during the treatment period will be analyzed using a Bayesian model for repeated measurements. The model may investigate effects for treatment (CFZ533 or placebo), time (visit week), baseline QMG score, treatment by time and baseline by time interactions.

Data analysis (cont'd)	
The target efficacy will be reached if at the end of the study, there is at least 90% probability that the difference between CFZ533 and placebo is <math>\geq 0</math> and 50% probability that the difference between CFZ533 and placebo is <math>\geq 3</math>.
 
The MGC composite is a key secondary endpoint. The changes from baseline in QMG scores at each visit of the treatment period (weeks 5, 9, 13, 17, 21 and 25) will be analyzed using a Bayesian model for repeated measurements.

Key words	CFZ533, Myasthenia Gravis

## 1 Introduction

### 1.1 Background

Acquired myasthenia gravis (MG) is an autoimmune disease that leads to fluctuating muscle weakness and fatigue. In the most common cases, muscle weakness is caused by circulating antibodies that bind to acetylcholine receptors at the postsynaptic neuromuscular junction, inhibiting the excitatory effects of the neurotransmitter acetylcholine.

The disease incidence is 3-30 cases per million per year and rising, most likely as a result of increased awareness. The prevalence of MG in the USA is estimated to be between 100 and 150 per million (Trough et al 2012). In MG, muscle weakness fluctuates with activity, and periods of rest offer only a temporary reprieve. The muscles that control eye and eyelid movement are particularly susceptible to weakness, but other muscles for chewing, talking, and swallowing are frequently involved. Patients may initially present with purely ocular MG, but this usually progresses to more severe, generalized disease with involvement of bulbar, axial, limb, and/or respiratory muscles (Trough et al 2012). It is important to distinguish MG from congenital myasthenic syndromes that can present with similar symptoms but are due to genetically determined defects in neuromuscular junction proteins, and do not respond to immunosuppressive treatments.

In MG, the autoantibodies most commonly act against the nicotinic acetylcholine receptor (nAChR), the receptor at the motor end plate for the neurotransmitter acetylcholine that stimulates muscular contractions. A minority of antibodies has specificity for the acetylcholine binding site and thereby directly impairs the ability of acetylcholine to bind to receptors. Others lead to the loss of functional receptors, either by complement fixation and focal lysis of the endplate region, or by inducing the muscle cell to eliminate the receptors through endocytosis (Ha and Richmond 2014).

Corporate Confidential Information

MG is treated medically with acetylcholinesterase inhibitors or immunosuppressants, and in selected cases, thymectomy. There is a high medical need in MG, and the disease can be life-threatening. In myasthenic crisis, patients can develop acute respiratory failure, due to paralysis of the respiratory muscles.

Corporate Confidential Information

The use of corticosteroids and other immunomodulatory drugs (e.g., azathioprine, cyclosporine, and mycophenolate mofetil) have proven beneficial for some patients in the management of this disorder; however, the majority of the MG patients develop an increased risk of infections and other long-term complications (Mehndiratta et al 2014), therefore there is a medical need for new treatments.

Corporate Confidential Information

Several lines of evidence suggest that inhibition of the CD40-CD154 co-stimulation pathway can be beneficial for the treatment of MG. In the majority of MG patients (85%), the production of pathogenic antibodies targeting muscle acetylcholine receptors (anti-AChR antibodies) is T cell dependent (Meriggioli and Sanders 2009). Most of these patients have thymic pathology usually in the form of hyperplasia, characterized by a hyper-proliferative thymus and ectopic germinal center formation with an activated B cell signature, including prominent CD40-CD154 signaling (Le Panse et al 2006).

Corporate Confidential Information

Corporate Confidential Information  
CFZ533 are outlined in [Section 3.6](#)

Corp Risks and benefits of treatment with  
erata

## 1.2 Study purpose

This study is designed to preliminarily evaluate safety, tolerability, pharmacokinetics/pharmacodynamics and efficacy of CFZ533 as an add-on therapy to standard of care in patients with moderate to severe myasthenia gravis (MG).

The results of this study will provide preliminary data to evaluate a further development of CFZ533 in the treatment of MG.

## 2 Study objectives

### 2.1 Primary objective(s)

Objective(s)	Endpoint(s)
To evaluate the safety and tolerability of IV CFZ533 as an add-on therapy to standard of care in patients with moderate to severe MG throughout the study	

• AEs / SAEs

• Vital signs and body measurements

• ECGs

• Hematology, blood chemistry, urinalysis.

To evaluate the efficacy of IV CFZ533 as an add-on therapy to standard of care in patients with moderate to severe MG	

• Mean change from baseline in the QMG Score for Disease Severity after 24 weeks of treatment (primary endpoint).

• Mean changes from baseline in the MGC Score for Disease Severity after 24 weeks of treatment.

• Proportions of patients requiring rescue therapy (i.e. IV immunoglobulins or plasma exchange).

## 2.2 Secondary objective(s)

Objective(s)	Endpoint(s)
To evaluate the efficacy of IV CFZ533 using relevant MG related outcome measures throughout the 24 weeks treatment period	

• Mean Change from baseline in QMG Score and MGC Score.

• Proportion of patients with improvement by <math>\geq 3</math> points in QMG score.

• Proportion of patients with worsening by <math>\geq 3</math> points in QMG score.

• Proportion of patients intolerant to steroid taper.

• Proportion of patients who discontinued due to inefficacy or worsening.

To evaluate the decay in efficacy of IV CFZ533 using relevant MG related outcome measures throughout the 24 weeks follow-up period	
To evaluate changes in patient's quality of life (QOL) throughout the 24 weeks treatment period	Mean change from baseline in the MG-ADL and MG QOL-15.
To evaluate the PK of 2-hour IV infusion of CFZ533 at 10 mg/kg administered q4w for 6 doses	Free CFZ533 in plasma
To evaluate the PD of CFZ533 (CD40 saturation on B cells, extent/duration of target engagement)	Free CD40 on B cells, total CD40 on B cells and total soluble CD40 in plasma
To assess immunogenicity in CFZ533-treated patients and in placebo-treated patients (pre-existing anti-drug antibodies).	Quantitative analysis of anti-CFZ533 antibodies in plasma

### 3 Investigational plan

#### 3.1 Study design

This is a randomized double-blind, placebo controlled, non-confirmatory study to preliminarily evaluate the safety, tolerability, PK/PD, and efficacy of IV CFZ533 administered every four weeks (q4w) over a 24 week treatment period in patients with moderate to severe MG. The investigational drug or placebo will be administered in addition to standard of care therapy for MG.

Patients should remain on their standard of care therapies and the dose should be maintained at a constant level during the study ([Section 4.1](#) and [Section 6.10](#)). For patients that are receiving corticosteroids at baseline, a predefined steroid tapering will be allowed after achievement of minimal manifestations (MM) state ([Jaretzki et al 2000](#)).

[figure not shown]
Patients on cholinesterase inhibitors (CI) should remain on stable doses throughout the study, but CIs should not be taken for at **least 12 hours prior** to QMG and MG composite testing at each visit, in order to reduce fluctuations in performance on functional tests due to the temporary symptomatic effects associated with CI use.

For each patient, there will be two screening visits. Most of the screening assessments are done during Screening Visit 1 (Day -28 to Day -8), while Screening Visit 2 (Day -7 to Day -3) is performed to collect a blood sample to allow laboratory results (chemistry, hematology, and pregnancy test, if applicable) to be available prior to randomization on Day 1. All laboratory results, including the MG autoantibodies diagnostic test performed at screening, must be available prior to dosing (Day 1-Visit 3) and meet eligibility criteria. Once continued eligibility is confirmed, patients will be assigned a randomization number at Day 1 and receive CFZ533 or placebo via a 2-hour intravenous infusion. Patients will be dosed every four weeks (q4w) according to their randomization for a total of 6 doses on Day 1 ± 2 (Week 1), Day 29 ± 2 (Week 5), Day 57 ± 2 (Week 9), Day 85 ± 2 (Week 13), Day 113 ± 2

(Week 17) and Day 141 ± 2 (Week 21). The treatment period (24 weeks) will be followed by a safety follow-up period of other 24 weeks. The duration of the entire study including screening will be approximately 52 weeks.

An overview of the study design is given in [Figure 3-1](#):

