### 5.1 Contraception requirements

Please refer to inclusion criteria ([Section 4.1](#)) for details of contraception requirements for the study. In consideration of the patient population and overall risk benefit profile, women of childbearing potential must utilize highly effective contraception to avoid becoming pregnant while receiving CFZ533 and for 12 weeks after the last dose or until data from the reproductive toxicity studies suggest otherwise.

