**Table 5-1 Prohibited treatments**

Medication	Wash-out	Action to be taken
IVIg or plasma exchange	8 weeks prior to randomisation	Investigational treatment discontinued, but patient can remain in the study for the safety follow-up period
Oral or IV cyclophosphamide; IV corticosteroid bolus (dose higher than 1 mg/kg)	3 months prior to randomisation	Patient's discontinuation and EoS assessments to be undertaken
Belimumab	6 months prior to randomisation	Patient's discontinuation and EoS assessments to be undertaken
Rituximab	12 months prior to randomisation	Patient's discontinuation and EoS assessments to be undertaken

Medication	Wash-out	Action to be taken
Any other biologic or an investigational drug	1 month or five times the half-life, whichever is longer prior to randomisation	Patient's discontinuation and EoS assessments to be undertaken
Live vaccination	4 weeks prior to randomisation	Patient's discontinuation and EoS assessments to be undertaken

Please, refer to [Section 6.10](#) for standard of care treatment instructions (e.g. corticosteroids, immunosuppressants and cholinesterase inhibitors) and other concomitant treatments.

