## 6.9 Rescue medication

Rescue therapy (IVIg or plasma exchange) is instituted due to worsening of myasthenic weakness that in the opinion of the treating physician requires immediate therapy. This usually involves acute worsening of oropharyngeal or respiratory function so that compromise of the airway or ventilator function is judged to be imminent.

In case of rescue therapy, study treatment should be discontinued but the patient can remain in the study or for the safety follow-up period or at least complete the EoS visit (Visit 777) assessments.

Use of rescue medication must be recorded on the Concomitant medications/Significant non-drug therapies CRF after start of study drug.

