### 9.2.2 SAE reporting

To ensure subject safety, every SAE, regardless of causality, occurring after the subject has provided informed consent and until 30 days after the last study visit must be reported to Novartis **within 24 hours** of learning of its occurrence as described below. Any SAEs experienced after this should only be reported to Novartis if the investigator suspects a causal relationship to study treatment.

Recurrent episodes, complications, or progression of the initial SAE must be reported as follow-up to the original episode, regardless of when the event occurs. This report must be submitted **within 24 hours** of the investigator receiving the follow-up information. An SAE that is considered completely unrelated to a previously reported one should be reported separately as a new event.

Information about all SAEs (either initial or follow up information) is collected and recorded on the paper Serious Adverse Event Report Form. The investigator must assess the relationship to each specific component of study treatment (if study treatment consists of several drugs) complete the SAE Report Form in English, and send the completed, signed form by fax within 24 hours after awareness of the SAE to the local Novartis Drug Safety and Epidemiology Department, notifying the Clinical Trial Leader. Contact information is listed in the SOM.

The original copy of the SAE Report Form and the fax confirmation sheet must be kept with the source documentation at the study site. Follow-up information should be provided using a new paper SAE Report Form stating that this is a follow-up to a previously reported SAE.

Follow-up information provided should describe whether the event has resolved or continues, if and how it was treated, whether the treatment code was broken or not and whether the subject continued or withdrew from study participation. Each re-occurrence, complication, or progression of the original event should be reported as a follow-up to that event regardless of when it occurs.

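### All-causality SAE reporting ends 30 days after the last study visit, with no minimum after the last dose, so some early stoppers are covered for much less time than completers

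*Protocol*

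**What the plan says.** Protocol Section 3.1 schedules six infusions, the last on Day 141 (±2 days), within a 24-week treatment period. It then adds: "The treatment period (24 weeks) will be followed by a safety follow-up period of other 24 weeks".

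Section 9.2.2 sets the duty to report SAEs of any cause. It starts at consent and runs "until 30 days after the last study visit must be reported to Novartis". For later events: "Any SAEs experienced after this should only be reported to Novartis if the investigator suspects a causal relationship to study treatment". Neither sentence counts time from the last dose, and nothing else in the available text sets a minimum SAE period after it.

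Two routes take a patient who has stopped drug to the End of Study visit (Visit 777) without the full follow-up:

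- Rescue with IVIg or plasma exchange. Drug is stopped, and under Section 6.9 the patient "can remain in the study or for the safety follow-up period or at least complete the EoS visit". Section 5.2 allows the same choice.
- Any other prohibited treatment. Section 5.2 takes the patient out of the study with Visit 777 assessments; Table 5-1 gives the action as "Patient's discontinuation and EoS assessments to be undertaken".

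Section 7.1 asks for safety follow-up after a mandatory treatment stop where this can be done, but gives no duration. Section 9.5 separately requires SAEs during a pregnancy to be reported. SAP Section 8.1.2 tabulates the number and percentage of subjects with adverse events by treatment and describes no allowance for length of observation.

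**The concern.** Safety throughout the study is a primary objective, with AEs and SAEs among its endpoints (Protocol Section 2.1). Early exit may also be related to treatment: need for rescue, and discontinuation for inefficacy or worsening, are themselves efficacy endpoints (Sections 2.1 and 2.2). If early exit is more frequent in one arm, that arm's SAEs are sought over a shorter time, and crude percentages would understate its rate relative to the other.

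The reporting of suspected-related SAEs after the window does not fully replace all-causality reporting. The comparison between arms rests on events of any cause, and a blinded investigator may reasonably attribute a late infection to background immunosuppressants or to the disease. Infection matters here: Section 3.6 expects immunosuppression from the drug, and Section 3.1 gives infections special interest. Some hold criteria in Section 7.4, such as two patients with severe systemic infection, are also counted without requiring drug-relatedness. Such an event after the window has closed, if not suspected to be related, need not reach the sponsor.

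**Working it through.** Inputs, all from the Protocol except the lag d:

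- Screening from Day -28; treatment 24 weeks (168 days); follow-up 24 weeks (168 days); last dose Day 141 ± 2 (Section 3.1)
- All-causality SAE reporting to 30 days after the last visit (Section 9.2.2)
- 44 randomized, at least 36 expected to complete (Section 4)
- d, the days from last dose to an early Visit 777. This is an assumption, because Table 8-1 is not in the available text. The range shown is 0 (same day) to 28 (the next 4-weekly visit).

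**Check against the plan's own figure.** 28 + 168 + 168 = 364 days = 52.0 weeks. This agrees with Section 3.1: "The duration of the entire study including screening will be approximately 52 weeks".

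**Completer.** End of treatment: Day 1 + 168 = Day 169. End of follow-up: Day 169 + 168 = Day 337. From last dose to last visit: 337 − 141 = 196 days. All-causality cover after the last dose: 196 + 30 = 226 days. With the last dose on Day 143 or Day 139 this becomes 224 or 228.

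**Early stopper leaving through Visit 777.** Cover = d + 30 days.

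| d | Cover (days) | Shortfall against 226 | Share of a completer's cover |
|---|---|---|---|
| 0 | 30 | 196 | 30/226 = 13% |
| 14 | 44 | 182 | 44/226 = 19% |
| 28 | 58 | 168 | 58/226 = 26% |

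**Comparison with a dose-anchored period elsewhere.** The contraception rule in Section 5.1 runs "for 12 weeks after the last dose", which is 84 days. Cover falls below 84 days whenever d + 30 < 84, that is, d < 54. The difference is 84 − 30 = 54 days at d = 0 and 84 − 58 = 26 days at d = 28. This shows scale only, since that period was not set for SAEs.

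**How many.** 44 − 36 = 8, or 8/44 = 18%. This is an upper figure for expected non-completers, not a count of patients with short cover. It can include consent withdrawals, and not every non-completer leaves by these routes.

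**The case against.** Much of the case on the other side stands.

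- A reader might infer that the plan breaks its own 12-week post-dose safety standard. It does not. The 12 weeks in Section 5.1 concern contraception and may change with reproductive toxicity data. Section 5.2 contains a shorter post-dose interval, four weeks for prohibited treatments, and even 30 days exceeds that.
- A reader might infer that early stoppers have no SAE cover after the window. They do: suspected-related SAEs stay reportable with no end date (Section 9.2.2), patients are told to report possibly related events later (Section 9.1), and unresolved AEs are followed to resolution (Section 7.1).
- Pregnancy should not be counted as an exposed route, because Section 9.5 requires SAEs during pregnancy to be reported without a causality condition. Early termination of the study (Section 7.5) affects both arms at once and gives no clear imbalance.
- Section 7.1 asks for safety follow-up after mandatory treatment stops, and its list includes rescue, worsening and severe infection. Many of the patients of most concern may therefore stay under observation.
- The 30-day figure needs Visit 777 on the day of the last dose, and the true lag cannot be checked.
- The study is non-confirmatory and its safety analysis is descriptive.

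These points narrow the issue but do not remove it. Following a known event does not detect new ones. The request in Section 7.1 is conditional and has no duration, while Sections 5.2 and 6.9 let a rescued patient finish at Visit 777. For other prohibited treatments, exit is required.

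**Conclusion.** The gap is real but limited. No minimum SAE period is anchored to the last dose, so all-causality cover after it is about 226 days for completers and d + 30 days for those who leave through Visit 777: 30 to 58 days if d lies between 0 and 28. It applies mainly to patients given another prohibited treatment and to rescued patients who do not stay. The number affected is unknown.

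The documents do not support saying that 8 of 44 patients each lose 54 days: 8 is an upper figure for non-completers, and 54 needs both a same-day exit and a borrowed 12-week yardstick. Nor do they show that the arm comparison will be biased; that depends on exit rates differing by arm. What they support is that, if those rates differ, the crude percentages in SAP Section 8.1.2 would compare arms over unequal windows. For a primary safety objective, that is worth a small change.

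**What to change.** 1. In Protocol Section 9.2.2, collect all-causality SAEs until the later of 30 days after the last study visit and a stated minimum period after the last dose. The sponsor should choose and justify that period. Twelve weeks is one option, borrowed from the contraception rule in Section 5.1, and should not be presented as an existing SAE standard.
2. Where a patient has stopped visits without withdrawing consent, collect this by telephone. Patients who have withdrawn consent are outside the change (Section 7.3).
3. Reconcile Sections 5.2, 6.9 and 7.1 on what safety follow-up is intended after treatment stops.
4. In SAP Section 8.1.2, add one table of SAEs by arm within the common post-dose window. This aligns the period after the last dose; it does not equalise time on treatment, and the table should say so.

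The change affects data collection only. It costs one sentence in Section 9.2.2 and the alignment of existing text, made by amendment, a telephone contact for a few patients, and one extra table.
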